4.4 Independent Radiologist Assessment

An independent radiographic analysis will be performed to evaluate all images and assess subjects' radiographic status. The following quantitative and qualitative assessments will be performed.

4.4.1 Plate Location Measurements

Plate location measurements including the distance from end of plate to adjacent level at both the cephalad and caudal ends of the plate, distance from the point of screw insertion (center line of screw) to endplate of affected level at both the cephalad and caudal ends of the plate and screw angulation at both the cephalad and caudal ends of the plate at each time point will be assessed quantitatively using validated computer-assisted measurement tools.

4.4.2 Disc Height

Anterior and posterior disc height will be assessed quantitatively using validated computer-assisted measurement tools. Disc height will be calculated from neutral lateral radiographs. Anterior (posterior) disc height is defined as the distance between the anterior-inferior (posterior-inferior) corner of the superior vertebra, and the corresponding corner of the inferior vertebra. This distance is measured perpendicular to the superior endplate of the inferior vertebra. Average disc height is calculated as the simple average of the anterior and posterior disc heights. Disc Height will be reported in units of millimeters.

4.4.3 Change in Disc Height

Change in disc height is defined as the change in distance between the anterior-inferior (posterior-inferior) corner of the superior vertebra, and the corresponding corner of the inferior vertebra. This change is measured perpendicular to the superior endplate of the inferior vertebra. Change in average disc height is calculated as the simple average of the change in anterior and posterior disc heights. Change in disc height is calculated by subtracting the measured disc height at one time point from a baseline disc height measurement. The results will be recorded in units of millimeters.

4.4.4 Disc Degeneration

Disc Degeneration, including Adjacent Level Degeneration, will be qualitatively graded in accordance with the following definitions (adapted from Weiner et al ³, Lane et al ⁴ and Wilke et al ⁵):

0. **None:** No disc space narrowing, no osteophytes, no endplate sclerosis
1. **Mild:** < 33% disc space narrowing, mild osteophytes, no endplate sclerosis
2. **Moderate:** 33% - 66% disc space narrowing, moderate osteophytes, mild to moderate endplate sclerosis
3. **Severe:** ≥ 67% disc space narrowing, severe osteophytes or bridging, severe endplate sclerosis

It should be observed that Disc Degeneration is assessed from an evaluation of 3 component factors: Disc Space Narrowing, Osteophyte Formation, and Endplate Sclerosis. Disease severity will be defined by the most severe radiographic component.

4.4.5 Adjacent Level Ossification

The severity of adjacent level ossification will be measure on the last follow-up (24 month) lateral radiograph as:

- Grade 0 – None
- Grade 1 – Mild (if the ossification extended across <50% of the disc space)
- Grade 2 – Moderate (if the ossification extended across \geq 50% of the disc space)
- Grade 3 – Severe (if there is complete bridging of the adjacent disc space)

4.4.6 Fusion Determination

Fusion will be assessed by an independent radiographer when data collection is complete at each site. The radiographic report (if available) and the x-rays will be sent to an independent radiologist for review at the end of the study. X-rays will be evaluated at each visit for fusion determination. The grading system is as follows:

- Grade 1 - No graft incorporation
- Grade 2 - Incomplete graft incorporation
- Grade 3 - Graft Incorporation
- Grade 4 - Solid fusion with graft incorporation

Radiographic Success: Radiographic success is defined by graft incorporation or solid fusion with graft incorporation (Grade 3 or 4)

Radiographic Failure: Radiographic failure is defined by incomplete graft incorporation or no graft incorporation (Grade 1 or 2).

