4.3 Follow-up Assessment

Subjects will be asked to return postoperatively at 6 (\pm 2weeks), 12 (\pm 1 month) and 24 (\pm 1 month) months for a clinical and radiographic exam. Data collected during this exam will include:

- Clinical assessment: The investigator will carry out a clinical examination at the 6, 12 and 24 month visit to assess:
 - subject compliance with postoperative care instructions,
 - ability to return to work and normal activity, and

- any procedure related or device related adverse events since discharge from the hospital
- Subject self-assessment:
 - Each subject will be asked to complete a follow-up Neck Disability Index (NDI) form, SF-36 form and a Neck and Shoulder/Arm Pain VAS form at each follow-up visit.
- Radiographic assessment: Each subject will undergo AP, lateral and flexion extension x-rays at the 6, 12 and 24 month visit to assess:
 - Presence / absence of heterotopic bone at the fusion site or at adjacent vertebral levels
 - integrity of the device, with observation for events such as plate and/or spacer migration or subsidence, hardware fracture, and progress towards fusion consolidation

Findings from any additional imaging studies deemed necessary by the investigator will be recorded and reported with study results.

Published data from the current literature will be gathered for purposes of comparing operating room time and the surgeon's assessment of fusion compared with that reported in this study.

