5.1 Definition

A complication is any written, electronic, or oral communication that alleges deficiencies related to the identity, quality, durability, reliability, safety, effectiveness, performance, or any indication of the failure of a device to meet a user or customer's expectations. The complaint may be the possible failure of a device, labeling, or packaging to meet any of its specifications after it is released for distribution.

6 Primary Objective and Sample Size Justification

The primary objective of this study is to obtain a precise estimate of the proportion of patients who have moderate-to-severe adjacent-level ossification at 24 months, indicated by a severity of Grade 1, 2, or 3 at any level on the 24-month lateral radiograph. A point estimate and two-sided, 95% confidence interval for this endpoint will be calculated using the normal approximation to the binomial, as follows:

$$\hat{p} \pm z_{1-\frac{\alpha}{2}} \sqrt{\frac{\hat{p}(1-\hat{p})}{n}}$$

Where:

\hat{p} = the proportion of soft tissue masses found

n = the total number of patients

α = 0.05

The sample size for this study was based on the number of patients needed in order to calculate, within a precision of 10%, a 95% confidence interval for the proportion of patients with moderate-to-severe adjacent-level ossification. The “precision” of a confidence interval refers to the distance from the estimated proportion (point estimate) to the upper and lower limits of the confidence interval. The full width of the confidence interval is twice the precision. This sample size assumes that the rate of incidence will be approximately what was observed in a study conducted by Park, et.al². This study indicates that rate of incidence of moderate-to-severe adjacent-level ossification observed in this study for patients with a PDD of > 5mm is 45.5%. Under this assumption, a sample size of 96 patients will allow a precision of 10% to be achieved. Accounting for possible attrition of up to 15% gives a sample size of 113 patients.

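### Section 4.4.6 sends an earlier radiographic report, where one exists, to the independent radiologist without masking, so the fusion read may be influenced in some subjects and not others

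*Combined protocol and SAP*

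**What the plan says.** Section 4.4 sets the standard for the central read: "An independent radiographic analysis will be performed to evaluate all images and assess subjects' radiographic status". Plate location, disc height and its change, disc degeneration, adjacent-level ossification and fusion all sit under that heading.

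Section 4.4.6 describes how the fusion read is made. It begins: "Fusion will be assessed by an independent radiographer when data collection is complete at each site". The next sentence reads: "The radiographic report (if available) and the x-rays will be sent to an independent radiologist for review at the end of the study". The section goes on to grade fusion from 1 to 4, with Grades 3 and 4 counted as radiographic success and Grades 1 and 2 as failure.

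A second fusion read exists. Section 4.3 plans to gather published data for "comparing operating room time and the surgeon's assessment of fusion compared with that reported in this study", so the surgeon's opinion on fusion is also collected.

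Fusion is not the primary endpoint. Section 6 states the primary aim as to "obtain a precise estimate of the proportion of patients who have moderate-to-severe adjacent-level ossification at 24 months".

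**The concern.** An independent read is meant to give a grade formed apart from earlier opinions on the same films. Section 4.4.6 puts an earlier opinion in the reader's package and states no safeguard: no masking, no order of reading, no purpose for the report, and no log of which reads came with one.

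Two features make this more than a formality. First, the fusion scale has no measurable criteria. The line between failure and success is the line between incomplete graft incorporation and graft incorporation, and a prior opinion can most easily tip a borderline film there. Second, the report goes only where one exists. With up to 15 centers, some films would be read with an earlier opinion at hand and others without.

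At stake is the pooled fusion success percentage. The study has no concurrent control, so a reading bias has no comparison arm in which to cancel. If the report does come from the site, the independent read also loses part of its value as a check on the surgeon's assessment.

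**Working it through.** **1. The plan's own figures.** The only calculation in the plan is the sample size in Section 6, for the ossification proportion. Inputs: assumed rate 0.455, two-sided 95% interval, half-width 0.10, attrition 15%.

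- n = 1.96² × 0.455 × 0.545 / 0.10² = 95.26, rounded up to 96.
- 96 / (1 − 0.15) = 112.9, rounded up to 113.

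Both stated figures reproduce. This point changes neither of them.

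**2. Who wrote the report.** Section 4.4.6 does not say. Two readings are open:

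- *A site report.* This is likely, because the report is sent only if it exists and because surgeons assess fusion locally (Section 4.3).
- *A report by the independent radiographer.* The preceding sentence gives that person the fusion assessment when each site's data collection is complete. The next sentence gives a radiologist a review at the end of the study. These may be two successive reads, or one read described twice in different terms.

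On either reading the radiologist can receive an earlier interpretation of the same films.

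**3. Is the reader masked?** No section says that the report is withheld until the grade is recorded. Equally, no section says that it is consulted before or during grading. What is established is a missing safeguard; influence on the grade is a risk.

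**4. Which reads are exposed.** The sentence stands under Fusion Determination. The ossification grade (Section 4.4.5) is taken from the 24-month lateral film and belongs to the same independent analysis. One reader could handle one package for both, but no section says so. Plate location and disc height (Sections 4.4.1 and 4.4.2) use computer-assisted measurement, and change in disc height (Section 4.4.3) is calculated from measured heights. The judgement grades are in Sections 4.4.4 to 4.4.6.

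**5. Size.** Let f be the share of subjects with a report and d the change that seeing it makes in the chance of a success read. The observed success percentage then shifts by f × d. The documents give neither value. On assumed values:

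| f | d (points) | shift (points) |
|---|---|---|
| 0.25 | 5 | 1.25 |
| 0.50 | 10 | 5 |
| 1.00 | 20 | 20 |

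The sign of d is also unknown. Another way to count gives the share of grades altered. Assume that reader and report would disagree on 10% to 20% of films, half the films have a report, and the reader follows it in half of the disagreements. Then 0.10 × 0.5 × 0.5 = 2.5% to 0.20 × 0.5 × 0.5 = 5% of grades change. That is a gross count. Changes in opposite directions offset, and a move between Grades 1 and 2, or between 3 and 4, leaves success unchanged. With ranges this wide, resting wholly on assumed inputs, the size is undetermined.

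**The case against.** The strongest reply is that the report may be background, or may be meant for reconciliation after grading, and that Section 4.4.6 itself says x-rays are evaluated for fusion. Fusion has no sample-size basis, test or planned interval in Section 6, and Section 4.5 promises only tables and descriptive statistics. With one arm and no planned comparison between sites, unequal exposure biases no treatment contrast within the study.

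Much of this stands, and it limits what can be claimed. A reader might infer three stronger things that the documents do not support:

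- *That the reads are in fact anchored to the site's opinion.* Site authorship is an inference, and the protocol does not say that the report is read before grading.
- *That the primary ossification estimate is affected.* The sentence concerns fusion. No section uses the report for ossification or says that such reports grade it, and the ossification grades have anatomical cut-offs (less than half of the disc space, half or more, complete bridging).
- *That exposure could never be traced.* No log of what was sent is required, but Section 7.5 requires source records to be kept and Section 7.8 opens them to inspection. Whether a subject had a report should largely be recoverable.

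What the reply does not remove is the rule itself. The protocol directs that an earlier report go to the reader and states no restriction on its use. A descriptive percentage can still be biased, and use of the report for background or reconciliation remains possible after the grade is recorded.

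**Conclusion.** The point holds as a gap in the protection of the independent fusion read. Section 4.4.6 states a rule that weakens the independence promised in Section 4.4, because an available report of unstated authorship travels with the films and nothing masks the reader to it. The fusion grade may therefore be influenced in some subjects and not others. Reach to the 24-month ossification grade is possible only under an assumption about workflow that the protocol does not state.

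Neither the size nor the direction of any bias can be derived from the documents, and the sample-size figures stand. The case for acting rests on a judgement-based success boundary, the absence of a concurrent control, and a remedy that costs almost nothing. It is a free improvement and does not show that the results would be invalid.

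**What to change.** In Section 4.4.6, strike the report from the sentence so that only the x-rays go to the independent reader. Alternatively, keep it and state whose report it is, and that any earlier report is withheld until the reader's grades under Sections 4.4.4 to 4.4.6 have been recorded. In either case, settle whether the radiographer and the radiologist are one reader or two and use one term for each role. If they are two, say whose grade determines fusion success. Earlier reports can stay on file as source documents.

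Cost: one or two sentences in the protocol and a matching line in the image-transfer instructions. No extra reader, film or visit is needed. Section 4.4.6 places the reads at site completion or at the end of the study, so the change can be made before they begin.

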4.5 Post Validation Follow-Up Meeting

Upon completion of the post market surveillance, the sponsor will compile the results and organize a meeting in of all participating clinicians to review and discuss the study results including the intra-operative assessment of instruments and implants and clinical outcomes of the MaxAn[®] Anterior Cervical Plate System. Tabular presentations of the data and descriptive statistics will be used to report outcomes.

4.6 Subject Withdrawal

It is recognized that the subject's participation in this post market surveillance study is entirely voluntary, and that he or she may refuse to participate and may withdraw from participation at any time without jeopardy to any future medical care. It is also recognized that the surgeon, at his/her discretion, may withdraw a subject from this post market

surveillance study based upon his/her professional judgment. If the subject is withdrawn a final evaluation form will be completed.

Other Conditions for Withdrawal:

Any subject who develops a severe concurrent medical illness during the post market surveillance study should be withdrawn. This type of illness is defined as any illness that would hinder the subject's ability to return for scheduled follow-up appointments. Such a withdrawal will not be counted for the purposes of determining success or failure.

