5 COMPLICATIONS

In addition to the standard operating procedures for reporting complications per hospital/physician protocol, all clinical events, including both observed or volunteered problems, complaints, symptoms, physical signs or disease which either occur during the study, having been absent at baseline, or, if present at baseline, appear to worsen during the clinical outcomes collection study are to be recorded as complications in the subject's medical record and on the appropriate case report form. In addition for any cleared device, a Product Experience Report (PER) must be completed per the manufacturer's customary complaint procedure (SOP 114.0.1 – Product Complaint Procedure).

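### The illness-withdrawal rule in Section 4.6 turns some obtainable 24-month films and visit-based safety data into avoidable, health-related missing data

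*Combined protocol and SAP*

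**What the plan says.** The rule is in Section 4.6 (Subject Withdrawal), under Other Conditions for Withdrawal. It reads "Any subject who develops a severe concurrent medical illness during the post market surveillance study should be withdrawn", and the trigger is then defined: "This type of illness is defined as any illness that would hinder the subject's ability to return for scheduled follow-up appointments". On analysis it says "Such a withdrawal will not be counted for the purposes of determining success or failure". Earlier in the same section there is one data provision for any withdrawal: "If the subject is withdrawn a final evaluation form will be completed". Nothing in the protocol describes contact, imaging or complication follow-up after that form.

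Three other places bear on the consequence:

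- **Section 6 (Primary Objective and Sample Size Justification)** ties the primary endpoint to one film: "indicated by a severity of Grade 1, 2, or 3 at any level on the 24-month lateral radiograph". It defines n as all patients and gives no rule for a missing film.
- **Section 4.3 (Follow-up Assessment)** has the investigator ask at the 6, 12 and 24 month examinations about "any procedure related or device related adverse events since discharge from the hospital".
- **Section 5 (Complications)** covers events "which either occur during the study, having been absent at baseline", or worsening from baseline.

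Success and failure are defined only in Section 4.4.6, for fusion: Grades 3 and 4 are success, Grades 1 and 2 failure.

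**The concern.** The label in Section 4.6 is severe concurrent illness, but the definition sets no severity threshold and does not require that visits be impossible. An illness that makes attendance harder is enough. The rule therefore reaches subjects who could still come for a film at 24 months or answer a telephone call.

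The plate is implanted once, and Section 4.2 leaves postoperative care to each institution's standard. Withdrawal from this study stops no treatment; it stops data collection. For the primary endpoint, a subject withdrawn before 24 months has no film to grade. For safety, the scheduled questioning in Section 4.3 ends. For fusion, which is graded at every visit, the sentence on counting could remove 6 or 12 month grades already in hand.

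This missingness depends on health and is created by the protocol. The 15% attrition allowance protects the width of the interval, not the estimate against selective loss, and Section 6 plans no sensitivity analysis.

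**Working it through.** **1. The plan's own figures (Section 6).** Inputs: p = 0.455, half-width d = 0.10, two-sided 95% (z = 1.96), attrition 15%.

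- n = z² p(1 − p)/d² = 1.96² × 0.455 × 0.545 / 0.01 ≈ 95.26, rounded up to 96.
- 96 / 0.85 = 112.9, rounded up to 113.

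Both stated figures reproduce.

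**2. What the rule does to each data stream.**

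| Data | Where it comes from | After an illness withdrawal |
|---|---|---|
| Ossification (primary) | 24-month lateral film only (4.4.5, 6) | No film if withdrawn before 24 months |
| Adverse events at visits | 6, 12, 24 month examinations (4.3) | Scheduled questioning ends |
| Status at withdrawal | Final evaluation form (4.6) | Captured once |
| Fusion success or failure | Graded at each visit (4.4.6) | Not counted, so earlier grades may be dropped |
| Ossification denominator | n is all patients (6) | Not stated |

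**3. Precision.** Half-width = 1.96 × √(0.455 × 0.545 / n). The number of films recoverable by changing the rule is not in the documents, so the range is shown from none to all 17 planned losses (113 − 96).

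| Films recovered (assumed) | n | Half-width, points |
|---|---|---|
| 0 | 96 | 9.96 |
| 8 | 104 | 9.57 |
| 17 | 113 | 9.18 |

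The precision target is met even with none recovered. Precision is not the problem.

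**4. Bias.** If a share w is withdrawn and its true rate differs by Δ from the rate in the rest, the estimate from the rest is off by w × Δ. The documents give neither w nor Δ. With an assumed Δ of 20 points:

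- w = 5%: 0.05 × 20 = 1 point
- w = 10%: 0.10 × 20 = 2 points
- w = 15%: 0.15 × 20 = 3 points

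The sign follows the sign of Δ, and the bias is zero if Δ is zero.

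**5. Worst-case bound for all attrition.** Take 96 films observed with 44 positive (0.455 × 96 = 43.7, rounded) and 17 missing.

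- All missing negative: 44/113 = 38.9%.
- All missing positive: (44 + 17)/113 = 61/113 = 54.0%.

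This covers losses from every cause at the full 15% allowance. It shows what the attrition allowance leaves open, not what the illness rule alone does.

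**The case against.** There are several good points on the other side.

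- **The wording is softer than a mandate.** The protocol says these subjects should be withdrawn and calls the illness severe and concurrent. Concurrent reads naturally as separate from the surgery, so a reader who infers that procedure- or device-related illness is deliberately swept in goes beyond the text, which is silent on it. The definition is still loose enough for a site to apply it to any illness that impedes travel.
- **Sections 4.6 and 5 do not contradict each other.** Section 5 asks for "symptoms, physical signs or disease which either occur during the study" to be recorded. A site can record the illness as a complication and then withdraw the subject. What is lost is what happens afterwards.
- **Device events do not all go unseen.** Status at withdrawal is captured on the final form. Section 5 adds study recording to the usual hospital reporting and requires a product experience report, and the Reports subsection (printed as 6.2) requires reports of unanticipated adverse device effects. The loss is of scheduled, visit-based ascertainment.
- **Exclusion from the primary proportion is an inference.** Success and failure are defined only for fusion, and nothing removes a subject who has a 24-month film from the ossification estimate. The established effect on the primary endpoint is that the film may never be taken.
- **The size is modest and unknown.** Some of these subjects would miss the 24-month visit anyway, and 1 to 3 points is small against a planned half-width of 10.

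These points limit the claim but do not remove it. The rule as written still directs sites to stop collecting data that some subjects could give, with no plan for the loss.

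**Conclusion.** The point holds in a limited form. Section 4.6 creates avoidable, health-related missing data among subjects who could still attend or be contacted, and may discard fusion grades already obtained. Whether its counting rule reaches the ossification denominator is unstated and should be settled.

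The 1 to 3 point bias rests on an assumed 20-point difference and an assumed 5 to 15% withdrawn. Two stronger readings are not supported. First, a reader might take 38.9% to 54.0% as the effect of this rule; it is a worst-case bound for all-cause attrition of 15% and would exist without the rule. Second, a reader might infer that losing sicker subjects biases the ossification rate in a known direction; the documents give no link between concurrent illness and ossification, so the direction is unknown.

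The case for change rests on the loss being avoidable at little cost, not on a demonstrated large bias.

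**What to change.** Amend only the Other Conditions for Withdrawal paragraph of Section 4.6:

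- Treat an illness that hinders attendance as a missed visit, with the reason recorded, not as withdrawal from the study.
- Unless consent is withdrawn, obtain the 24-month lateral film when the subject is able, and collect complications to 24 months.
- Replace the sentence on not counting with a statement that all available fusion grades and 24-month films are analysed, and that the number of subjects without a 24-month film is reported by reason.

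Leave withdrawal of consent and withdrawal at the surgeon's discretion as they stand. The change affects data collection and analysis only and alters no treatment. It costs a protocol wording amendment and a small extra site effort to keep contact with a few subjects.
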